Oligohidrosis (decreased sweating) and hyperthermia, infrequently resulting in hospitalization, has been reported in clinical studies and post-marketing reports in association with the use of topiramate. These cases were characterized by decreased sweating and an elevation in body temperature above normal. Some of the cases were reported after exposure to elevated environmental temperatures. The majority of the reports have been in children. Skin erythema has been reported secondary to the hyperthermia and oligohidrosis and should be monitored; adequate hydration is encouraged.

Hyperammonemia and Encephalopathy

In clinical studies and post-marketing reports, concomitant administration of topiramate and valproic acid has been associated with hyperammonemia with or without encephalopathy in subjects who have tolerated either drug alone. In most cases, symptoms and signs abated with discontinuation of either drug. This adverse event is not due to a PK interaction.

Topiramate treatment has produced hyperammonemia (in some instances dose-related) in clinical studies in adolescents (12-16 years of age) who were treated with topiramate monotherapy for migraine prophylaxis and in very young pediatric subjects (1-24 months of age) who were

treated with adjunctive topiramate for POS. In some subjects, ammonia was markedly increased (defined in the clinical study report as >50% increase from baseline and absolute value >2x upper limit of normal [ULN]). In the adolescent subjects, the incidence of markedly increased hyperammonemia was 3% (1 subject), 0%, and 9% (3 subjects) for the placebo, 50 mg/day, and 100 mg/day groups, respectively.¹⁰

The hyperammonemia associated with topiramate treatment occurred with and without encephalopathy in placebo-controlled studies, and in an open-label extension study in infants. Dose-related hyperammonemia was also observed in the open-label extension study in pediatric subjects 1 month to 2 years of age. Clinical symptoms of hyperammonemic encephalopathy may include acute alterations in level of consciousness and/or cognitive function with lethargy or vomiting. Hyperammonemia with and without encephalopathy has also been observed in post-marketing reports in patients who were taking topiramate without concomitant valproic acid.³⁸

Kidney Stones

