13. Subject has clinically relevant abnormalities noted on renal ultrasound or DEXA scans. Subjects with baseline BMD Z-scores ≤ -2 , for either posterior-anterior lumbar spine (L1-L4) or total body less head, will not be enrolled.
14. Subject has congenital glaucoma or known ocular deficits, or is receiving any ocular medications except lubricating eye drops or topical antibiotics.
15. Subject has a known history of central hyperthermia, dysautonomia, or other disturbances of autonomic function.
16. Subject has a known history of inborn errors of metabolism, mitochondrial dysfunction, or prior evidence of hyperammonemia.

-
17. Subject has any clinically significant abnormality in laboratory tests at screening, including but not limited to:
 - WBC count $<3,000/\mu\text{L}$ or absolute neutrophil count $<1,000/\mu\text{L}$ in the last 6 months
 - Aspartate aminotransferase (AST), alanine aminotransferase (ALT), or gamma-glutamyltransferase (GGT) ≥ 3 times the ULN
 - Total bilirubin ≥ 1.5 mg/dL or conjugated bilirubin $\geq 20\%$ of total
 - Venous ammonia ≥ 2 times the ULN
 - 25-hydroxy-vitamin D (level for clinically significant vitamin D deficiency is <12.0 ng/mL, conventional units [<30 nmol/L, SI units])^{19,42}
 - Parathyroid hormone (normal reference range is 14.0 to 72.0 pg/mL)
 - 1,25-dihydroxy-vitamin D, as determined by the age-dependent reference ranges (see lab manual)
 - Insulin-like growth factor 1 (IGF-1), as determined by the age-dependent reference ranges (see lab manual)
 18. Subject has a bicarbonate level <20 mEq/L, has a diagnosis of metabolic acidosis, or is on alkali therapy.
 19. Subject has refractory epilepsy and requires adjunctive AED therapy or is receiving >1 concurrent AED (including benzodiazepines, regardless of the reason for prescription).
 20. Subject is being treated with furosemide, hydrochlorothiazide, vigabatrin, vitamin B₆ therapy for epilepsy, monoamine oxidase (A or B) inhibitors, felbamate, zonisamide, or any other medication that is a potent carbonic anhydrase inhibitor (eg, acetazolamide). Past treatment with furosemide for more than 2 weeks must be discussed with the sponsor and the discussion documented.

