a The optional use, during the screening period, of local laboratory evaluations for 25-hydroxy-vitamin D, 1,25-dihydroxy-vitamin D, Parathyroid hormone (intact) and IGF-1 might lead to an increase in blood volume for the subject concerned. The total volume is dependent on the local laboratory requirements and on the number and type of individual assays.

b Calculated as number of samples multiplied by amount of blood per sample.

c All laboratory tests will be evaluated centrally except for venous ammonia, which will be evaluated locally (except in select countries where local testing is not possible, in which case the central laboratory will also evaluate venous ammonia). The laboratory tests for 25-hydroxy-vitamin D, 1,25-dihydroxy-vitamin D, Parathyroid hormone (intact) and IGF-1 at screening will be evaluated centrally but additional evaluation at local laboratory is allowed to reduce the duration of the screening phase. At the discretion of the investigator, one, or more of these laboratory parameters may be evaluated at the local laboratory. The volume of blood is based on reference laboratory minimal volumes.

AED=antiepileptic drug; CBC=complete blood count; EDTA= ethylene diamine tetra-acetic acid; IGF-1=insulin-like growth factor 1.

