Blood samples for serum chemistry (nonfasting) and hematology and a random urine sample for urinalysis will be collected. The investigator must review the laboratory report, document this review, and record any clinically relevant changes occurring during the study in the adverse event section of the CRF. The following tests will be performed by the central laboratory except for venous ammonia, which will be evaluated locally (except in select countries where local testing is not possible, in which case the central laboratory will also evaluate venous ammonia). The laboratory tests for 25-hydroxy-vitamin D, 1,25-dihydroxy-vitamin D, Parathyroid hormone (intact) and IGF-1 at screening will be performed at a central laboratory, but additional evaluation at local laboratory is allowed in order to reduce the duration of the screening phase:

- Hematology Panel
 - hemoglobin
 - hematocrit
 - red blood cell count
 - WBC count with differential
 - platelet count

- Serum Chemistry Panel

-sodium	-creatine phosphokinase
-potassium	-lactic acid dehydrogenase
-chloride	-uric acid
-bicarbonate	-calcium
-blood urea nitrogen (BUN)	-phosphorus
-creatinine	-albumin
-glucose	-total protein
-AST	-cholesterol
-ALT	-triglycerides
-GGT	-magnesium
-total bilirubin	-25-hydroxy-vitamin D*
-ammonia	-1,25-dihydroxy-vitamin D*
-serum pregnancy test (at screening, for girls of childbearing potential)	-parathyroid hormone*
-alkaline phosphatase	-IGF-1*

* Only measured at visits for screening, Month 6, and Month 12/early withdrawal (see Bone Mineralization section below).

- Special instructions for ammonia sample collection: Collect blood on ice, separate plasma from cells, and freeze ASAP (within 15 minutes of draw time). Specimens need to be spun in a refrigerated centrifuge and are unstable if thawed and refrozen.
- In addition to its routine assessment, free-flowing venous ammonia will be obtained on an immediate basis in the event of:
 - Clinical evidence of change in mental status consistent with a hyperammonemic encephalopathy (not seizures or post-ictal state)
 - Elevated hepatic enzymes as follows, unless a routine ammonia done at the same time was normal:
 - ALT, AST, or GGT ≥ 3 times the ULN (or ≥ 2 times the ULN for subjects taking valproic acid)
 - Total bilirubin ≥ 1.5 mg/dL
 - Conjugated bilirubin $\geq 20\%$ of the total
 - Any other appropriate clinical indication

- 25-hydroxy-vitamin D, 1,25-dihydroxy-vitamin D, Parathyroid hormone (intact) and IGF-1:

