17.2.2. Required Prestudy Documentation

The following documents must be provided to the sponsor before shipment of study drug to the investigational site:

- Protocol and amendment(s), if any, signed and dated by the principal investigator
- A copy of the dated and signed, written IEC/IRB approval of the protocol, amendments, informed consent form, assent forms, any recruiting materials, and if applicable, subject compensation programs. This approval must clearly identify the specific protocol by title and number and must be signed by the chairman or authorized designee.
- Name and address of the IEC/IRB, including a current list of the IEC/IRB members and their function, with a statement that it is organized and operates according to GCP and the applicable laws and regulations. If accompanied by a letter of explanation, or equivalent, from the IEC/IRB, a general statement may be substituted for this list. If an investigator or a member of the investigational staff is a member of the IEC/IRB, documentation must be obtained to state that this person did not participate in the deliberations or in the vote/opinion of the study.
- Regulatory authority approval or notification, if applicable
- Signed and dated statement of investigator (eg, Form FDA 1572), if applicable
- Documentation of investigator qualifications (eg, curriculum vitae)
- Completed investigator financial disclosure form from the principal investigator, where required
- Signed and dated clinical trial agreement, which includes the financial agreement
- Any other documentation required by local regulations

The following documents must be provided to the sponsor before enrollment of the first subject:

- Completed investigator financial disclosure forms from all clinical subinvestigators
- Documentation of subinvestigator qualifications (eg, curriculum vitae)
- Name and address of any local laboratory conducting tests for the study, and a dated copy of current laboratory normal ranges for these tests, if applicable
- Local laboratory documentation demonstrating competence and test reliability (eg, accreditation/license), if applicable

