7.10. Clinical Laboratory Tests

Figures of the mean change from screening (+/- Standard Error) values in continuous hematology, urinalysis and serum chemistry laboratory parameters will be presented by visit. The observed and change from baseline values of lab parameters will also be summarized by visit. For calculation, the signs “<” or “>” will be removed and resulting numerical value will be used. The reference ranges for labs from the SAP will be used, not the reference ranges provided from the Covance.

The shift table of pre- vs. post-treatment with classes for below, within, and above normal ranges will be presented.

The number and percentage of subjects with markedly abnormal (low, high) laboratory hematology, urinalysis/24-hour urine and serum chemistry parameters during the study (from treatment start to 30 days after last dose or the end of treatment visit date, whichever is later) that were not present at baseline will be provided. [Appendix 2](#) presents the markedly abnormal criteria. The conversion factors for 25 Vitamin D, 1, 25 Vitamin D and PTH are also listed.

The laboratory data will be listed. The subjects with any laboratory results outside the reference ranges and the subjects with any markedly abnormal laboratory results will be listed.

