Appendix 2: Markedly Abnormal Laboratory Parameter Values

Chemistry

Laboratory Value (SI Unit)	Lower Limit of Normal (LLN) Range	Upper Limit of Normal (ULN) Range	DNP Recommended Markedly Abnormal: Low	DNP Recommended Markedly Abnormal: High
Alanine Amino Transferase – ALT (SGPT)(U/L)	1	30	NA	$\geq 3 \times \text{ULN}$, OR $\geq 5 \times \text{ULN}$, OR $\geq 10 \times \text{ULN}$
Aspartate Amino Transferase - AST (SGOT)(U/L)	0	35	NA	$\geq 3 \times \text{ULN}$, OR $\geq 5 \times \text{ULN}$, OR $\geq 10 \times \text{ULN}$
Albumin(g/L)	<5 years: 29 ≥ 5 years: 31	<5 years: 58 ≥ 5 years: 54	<5 years: ≤ 20 ≥ 5 years: ≤ 25	<5 years: ≥ 65 ≥ 5 years: ≥ 60
Alkaline Phosphatase(U/L)	Females: 2-10 years: 100 11-17 years: 100 ≥ 18 years: 30 Males: 2-10 years: 100 11-17 years: 100 ≥ 18 years: 30	Females: 2-10 years: 320 11-17 years: 320 ≥ 18 years: 120 Males: 2-10 years: 320 11-17 years: 390 ≥ 18 years: 120	NA	$> 3 \times \text{ULN}$
Ammonia(umol/L)	≤ 18 years: 21 ≥ 18 years: 0	≤ 18 years: 50 ≥ 18 years: 35.7	NA	$\geq 1.5 \times \text{ULN}$
Bicarbonate/			Value < 17, OR	

Laboratory Value (SI Unit)	Lower Limit of Normal (LLN) Range	Upper Limit of Normal (ULN) Range	DNP Recommended Markedly Abnormal: Low	DNP Recommended Markedly Abnormal: High
Carbon Dioxide (CO ₂) (mmol/L)	20	26	(Value < 17 and decrease from pre-treatment baseline > 5 when pre-treatment baseline ≥ 20)	≥ 31
Bilirubin – Total (umol/L)	1.7	20.5	NA	≥ 41
Blood Urea Nitrogen (BUN) (mmol/L)	2.5	7.9	NA	≥ 16
Calcium (mmol/L)	2	2.6	≤ 1.7	≥ 3
Chloride (mmol/L)	96	109	NA	≥ 112 OR ≥ 115
Total Cholesterol (mmol/L)	≤ 18 years: 0 ≥ 18 years: 0	≤ 18 years: 5.18 ≥ 18 years: 6.2	NA	≥ 1.2 X ULN
Creatinine (umol/L)	2-12 years: 27 13-17 years: 44 ≥ 18 years: Males 53 Females	2-12 years: 62 13-17 years: 88 ≥ 18 years: Males 115 Females	NA	≥ 1.6 X ULN

	44	106		
Creatine Kinase (CK) (U/L) – collected only in TOPMAT-MIG-3006	Females:	Females:	NA	≥ 1.6 X ULN
	0-3 years:	0-3 years:		
	18	134		
	4-6 years:	4-6 years:		
	18	147		
	7-9 years:	8-9 years:		
	18	295		
	10-12 years:	10-12 years:		
	18	184		
	13-15 years:	13-15 years:		
	18	187		
	16-17 years:	16-17 years:		
	18	169		

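### At the SAP's pediatric ULN, eligible children with baseline ammonia of 75 to <100 umol/L cannot enter the markedly abnormal table, however far they later rise

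*SAP*

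**What the plan says.** - **Enrolment.** Protocol 4.2, criterion 17, excludes a child whose venous ammonia at screening is 2 x ULN or more. It does not say whose ULN. Criterion 16 separately excludes earlier evidence of hyperammonemia, without a number.
- **Flag.** SAP Appendix 2 (Chemistry) gives one ammonia range for the whole trial population, 21 to 50 umol/L, and a markedly abnormal high limit of 1.5 x ULN or more. There is no change-from-baseline condition.
- **Counting rule.** SAP 7.10 gives the number and percentage of subjects with markedly abnormal values on study that were absent at baseline. Its shift table has three classes: below, within and above normal.
- **Baseline.** SAP 3.1 takes the last value up to Day 1. The Time and Events Schedule has laboratory tests at screening and none on Day 1, so in practice this is the screening sample.
- **Ranges.** SAP 7.10: "The reference ranges for labs from the SAP will be used, not the reference ranges provided from the Covance". Protocol 9.3 has the central laboratory run the tests "except for venous ammonia, which will be evaluated locally", apart from some countries where local testing is not possible.
- **Earlier definition.** Protocol section 1 (Hyperammonemia and Encephalopathy) quotes an earlier study's definition of a marked increase: ">50% increase from baseline and absolute value >2x upper limit of normal".

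**The concern.** The flag sits below the level at which a child is kept out of the trial, and a child flagged at baseline is left out of the emergent count. Together these rules create a group of eligible children for whom the categorical ammonia table can record nothing. They have the highest starting values, and hyperammonemia is a named event of interest for topiramate (Protocol 11.4, SAP 7.9). A reader who takes the markedly abnormal percentage as the rate of important on-treatment ammonia rises would not know that worsening in these children is missing.

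A second, smaller gap is that ammonia is the one routine analyte measured mainly in local laboratories, yet the sentence on reference ranges names only the central laboratory. The SAP does not spell out which ULN applies to a local ammonia result.

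**Working it through.** **1. Do the Appendix 2 multiples use the SAP's own ranges?** Appendix 2 gives no absolute ammonia limit, but it works through glucose. From the SAP range: 0.8 x 3.3 = 2.64 (printed 2.6), 1.2 x 5.8 = 6.96 (7.0), 0.8 x 3.9 = 3.12 (3.1), 1.2 x 6.4 = 7.68 (7.7). All four reproduce, so the ammonia multiple applies to the SAP ULN of 50.

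**2. The two limits at ULN 50.**
- Flag: 1.5 x 50 = 75 umol/L.
- Enrolment: 2 x 50 = 100 umol/L.
- Eligible under criterion 17 but already flagged: 75 to <100 umol/L.

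**3. What the tables record at ULN 50 (illustrative children).**

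| Baseline to on-study value | Markedly abnormal count | Shift table |
|---|---|---|
| 49 to 75 | counted | within to above |
| 60 to 90 | counted | above to above |
| 90 to 180 | not counted | above to above |

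The third child doubles and is not counted. The second shows that a raised baseline below 75 can still count.

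**4. How the band depends on the ULN used for enrolment, E.** The band is 75 to <2E, so it exists only if 2E > 75, that is E > 37.5. The documents give no local ULNs, so the values of E below other than 50 are assumptions. The figure 35.7 is Appendix 2's adult ULN.

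| E (umol/L) | 2E | Eligible and already flagged |
|---|---|---|
| 35.7 | 71.4 | none |
| 40 | 80 | 75 to <80 |
| 50 | 100 | 75 to <100 |
| 60 | 120 | 75 to <120 |

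**5. Local ranges.** Let L be the reporting laboratory's ULN. A locally normal result is above the SAP range only if L > 50, and markedly abnormal only if L is at least 75. If L < 50 the error reverses: at L = 40, results from 1.5 x 40 = 60 to <75 reach 1.5 times the local ULN but are not flagged.

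**6. What an added row would catch.** Take >2 x ULN with a >50% rise, at ULN 50. The child going from 90 to 180 qualifies: 180 > 100, and the rise is 90/90 = 100%. For baselines in the band the 50% condition is the binding one. A child at 75 must exceed 1.5 x 75 = 112.5, and a child at 90 must exceed 135.

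**The case against.** The strongest reply is that the main ammonia analysis is untouched. Protocol 11.4 lists change from baseline in ammonia among the key safety endpoints, and SAP 7.10 summarizes observed values and changes by visit without using a ULN or dropping anyone. A child in the band also appears in the laboratory and markedly abnormal listings, and SAP 7.9 counts adverse events that worsen as well as those that start. All of this stands. A reader might infer that children with raised baselines can never count; that is too broad. The gap is in one table, for baselines of 75 or more, plus a shift table too coarse to help.

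A reader might also infer that normal local results will be called markedly abnormal. The documents do not show this: it needs a local ULN of at least 75, none is given, and a low local ULN produces the opposite error. Nor is bias between arms shown. Randomization is stratified by country, and SAP section 7 plans no formal testing.

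Nothing is contradicted either. Protocol 11.4 leaves the markedly abnormal criteria to the SAP, Appendix 2 heads its limits as DNP recommended, and the earlier definition belongs to another study. Eligibility and reporting limits may properly differ. The earlier rates of 3%, 0% and 9% come from adolescents with migraine on placebo, 50 or 100 mg/day, so sharing a definition would not make the rates comparable.

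Finally, criterion 16 and the general wording of criterion 17 on clinically significant abnormalities may remove some children in the band. What remains is that the stated counting rule hides worsening in any who are enrolled.

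**Conclusion.** The point holds as a limited gap in descriptive safety reporting. With the SAP ULN of 50 umol/L used for both limits, eligible children with baseline ammonia of 75 to <100 umol/L cannot enter the markedly abnormal number-and-percentage table, and the shift table does not show their worsening. Changes, listings and adverse events do. The number of children affected cannot be worked out from the documents and may be small. The band narrows as the enrolment ULN falls below 50 and is empty at 37.5 or less. Which ULN governs local ammonia results needs a sentence in the SAP; the size and direction of any local-range effect depend on ULNs that the documents do not give. This is a cheap improvement to one table and does not affect the key change-from-baseline endpoint.

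**What to change.** In SAP 7.10 and Appendix 2:

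1. Keep the row at 1.5 x ULN or more as it is.
2. Add a treatment-emergent ammonia row for all children whatever their baseline: above 2 x ULN with a rise of more than 50% from baseline. The SAP already uses a change component for bicarbonate and counts worsening for adverse events. The new row should not replace the existing one: at ULN 50 a child going from 20 to 95 umol/L meets the 75 limit but not the >100 limit.
3. State which ULN applies to locally assayed ammonia. Where local ranges are available, show each result as a multiple of the reporting laboratory's ULN, as a sensitivity display only.

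The cost is one extra table row and a sentence. The sensitivity display also needs local ranges in the analysis data. Protocol 17.2.2 asks sites for "a dated copy of current laboratory normal ranges for these tests", where applicable, but that is a document supplied before enrolment and not a dataset, so some collection work should be expected.

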1.2. Overall Rationale for the Study

Among its various pharmacologic actions, topiramate is a carbonic anhydrase inhibitor and may induce metabolic acidosis, and other changes (eg, hypocitraturia, hypercalciuria, and elevated urine pH) that may be associated with an increased tendency for kidney stone formation.⁴¹ Chronic metabolic acidosis may be associated with abnormal bone mineralization and/or homeostasis of vitamin D, calcium, or phosphorus. Childhood is a critical period for bone mineralization and growth. The effects of topiramate on growth, bone mineralization, and kidney stone formation have not been fully and systematically evaluated or well characterized in pediatric populations.

Preclinical juvenile rat studies demonstrated various clinical chemistry and bone findings (eg, changes in serum and urinary phosphate, decreased global BMD, decreased growth plate thickness) with topiramate treatment that raise concerns about long-term toxicities in pediatric patients.

This study will systematically assess the long-term safety of topiramate monotherapy compared with levetiracetam monotherapy; specific emphasis will be on metabolic acidosis related to topiramate therapy and its association with nephrolithiasis, BMD abnormalities, and delayed growth in children (2 to 15 years of age).

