At the discretion of the investigator, one or more of these laboratory parameters may be evaluated at the local laboratory to reduce the duration of the screening phase. In such instances, the local laboratory instructions should be followed and local reference ranges should be applied. The local laboratory results would be used for decision regarding randomization. The central laboratory evaluation results will be used for study data analysis. The additional use of a local laboratory might lead to an additional amount of blood volume to be drawn from the subject at screening.
- Urinalysis will be performed by the central laboratory, and will include dipstick and sediment as noted below. If dipstick result is abnormal, flow cytometry will be used to measure sediment. In case of discordance between the dipstick results and the flow cytometric results, the sediment will be examined microscopically.

Dipstick

-specific gravity
-pH
-glucose
-protein
-blood
-ketones
-nitrite

Sediment

-RBCs
-WBCs
-epithelial cells
-crystals
-casts
-bacteria

- Urine Pregnancy Testing (for girls of childbearing potential only) to be obtained at all visits after screening during the open-label treatment phase. If a girl starts menstruating and becomes of childbearing potential during the study, urine pregnancy tests should be obtained at all subsequent visits during the open-label treatment phase.
- 24-Hour Urine Collection: A 24-hour urine collection will be analyzed for pH, calcium, citrate, phosphorus, and creatinine levels. Collection instructions and storage conditions will be specified in the laboratory manual. A 14-day window on either side of the scheduled Month 6 visit will be allowed for 24-hour urine collection. The collection at Month 12 should be completed before the Month-12 visit as this evaluation should be obtained while the subject is still receiving study-drug therapy.

Additional use of local laboratories is allowed in cases where safety follow-up is time-critical and the central laboratory results are not expected before the need to take actions for safety reasons.

After consultation with the medical monitor, investigators may obtain additional laboratory assessments and/or advice from local medical consultants in the event of any clinically important safety concern.

Bone Age Radiograph

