7. SAFETY

The safety variables to be summarized include kidney stones, height, weight, BMD and bone mineral content (BMC), biochemical markers of bone mineralization, bone age XR, seizure counts, cognitive, developmental, and behavioral assessments, treatment-emergent AEs, Columbia-Suicide Severity Rating Scale (C-SSRS), cognitive, developmental and behavioral assessments (COGSTATE computerized battery and NEPSY Language scale; Vineland Adaptive Behavioral Scale, Child Behavior Checklist (CBCL)), clinical laboratory tests (hematology, chemistry, urinalysis, and 24-hour urine collection), vital signs and physical exam. Safety variables are to be tabulated by descriptive statistics (n, mean, median, SD, minimum, and maximum; or n and percent). No formal statistical testing is planned.

For markedly abnormal labs and vital signs, age will be calculated at each visit to determine the criteria. Similarly, Vineland, CBCL and Cogstate will be calculated by age at each visit.

Z-scores for weight and height will be calculated using the SAS programs provided by the Centers for Disease Control (CDC) for the calculation of the 2000 CDC growth charts. Z-scores for the BMD and BMC will be provided by the central DEXA reading center (Bioclinica).

Z-scores for the DEXA scans will be calculated locally at baseline only to determine eligibility for the study, and centrally for all statistical analyses. The Z-score calculation will take the DEXA machine and the subject's age, sex, height, and ethnicity into consideration. The reference databases for calculating the Z-scores are provided in the DEXA Manual for this study (please see the imaging charter of attachment 1 for more details).

Longitudinal endpoints will be analyzed using a mixed-model repeated measures (MMRM) analysis. An MMRM analysis is included as sensitivity analysis to explore longitudinal safety data and will be analyzed in the following order.

1. The model includes treatment group, study center, age group (4 age groups), visit, treatment-by-visit interaction, baseline measure, and baseline-by-visit interaction with the unstructured covariance matrix.
2. If this model experiences convergence issues, then the same model with compound symmetric matrix followed by AR1 will be explored instead of unstructured.

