11. URINALYSIS

Laboratory Value (SI Unit)	Lower Limit of Normal (LLN) Range	Upper Limit of Normal (ULN) Range	Markedly Abnormal: Low	Markedly Abnormal: High
PH	4.5	8	≤ 4	≥ 8
Specific Gravity	1.007	1.03	≤ 1.001	≥ 1.035

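### The SAP promises 24-hour urine abnormality counts but has no urine limits for four of the five analytes, classes a pH of 8.0 both ways, and states no units or creatinine scaling

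*SAP*

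**What the plan says.** Protocol 9.3 defines the collection: "A 24-hour urine collection will be analyzed for pH, calcium, citrate, phosphorus, and creatinine levels". It is scheduled at screening, Month 6 and Month 12 or early withdrawal. Protocol 1.2 explains why it matters, naming "hypocitraturia, hypercalciuria, and elevated urine pH" among the topiramate-induced changes that may favour stone formation.

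SAP 7 lists it as a safety variable, under "clinical laboratory tests (hematology, chemistry, urinalysis, and 24-hour urine collection". SAP 7.10 then plans three kinds of output that bear on it:

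- Continuous summaries: "The observed and change from baseline values of lab parameters will also be summarized by visit".
- A shift table of pre-treatment against post-treatment class (below, within or above normal).
- A markedly abnormal table: "The number and percentage of subjects with markedly abnormal (low, high) laboratory hematology, urinalysis/24-hour urine and serum chemistry parameters during the study", restricted to abnormalities absent at baseline.

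On limits, SAP 7.10 says that Appendix 2 "presents the markedly abnormal criteria" and adds: "The reference ranges for labs from the SAP will be used, not the reference ranges provided from the Covance". The urine limits are in the short urinalysis table after Appendix 2. It has two rows. One is pH, with normal range 4.5 to 8, markedly low at 4 or less and markedly high at 8 or more. The other reads "Specific Gravity 1.007 1.03 ≤ 1.001 ≥ 1.035".

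**The concern.** Two of the three urine abnormalities that the protocol links to stones, low citrate and high calcium, have no definition in the limits that the SAP says it will use. The third, raised pH, has a definition that overlaps its own normal range. Without units or a derivation, a reader of the calcium and citrate tables also cannot tell whether a change reflects excretion, urine volume, body size or an incomplete collection.

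These tables support the stone question. SAP 7.1 reports stones themselves only as a descriptive percentage by arm, and SAP 1 records that enrolment stopped early, so the number of children in whom a stone could be seen is smaller than planned.

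**Working it through.** No sample-size or power figure underlies this point. The check compares the stated rules with each other.

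**1. Analytes against limits.**

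| 24-hour analyte (Protocol 9.3) | Row in SAP urine table | Other row in Appendix 2 |
|---|---|---|
| pH | yes | none |
| calcium | no | Chemistry only (2 to 2.6 mmol/L) |
| citrate | no | none |
| phosphorus | no | Chemistry only |
| creatinine | no | Chemistry only |

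The Chemistry rows match the serum panel in Protocol 9.3 and are not urine limits. Analytes without a urine limit: 5 − 1 = 4. That credits the pH row to the 24-hour sample. The row sits beside specific gravity, which Protocol 9.3 lists as a dipstick item, and the SAP does not say which sample it governs. If it is dipstick only, the count is 5 − 0 = 5. Because SAP 7.10 rules out the laboratory's ranges, there is no fallback for either the shift table or the markedly abnormal table.

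**2. Do markedly abnormal limits fall inside the normal range?** There is overlap if markedly high ≤ upper normal, or markedly low ≥ lower normal.

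- Specific gravity: 1.035 > 1.03 and 1.001 < 1.007, so no overlap.
- pH, low side: 4 < 4.5, so no overlap.
- pH, high side: 8 ≤ 8, so overlap at exactly 8.0.

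| pH reading | Shift table (4.5 to 8 is within) | Markedly high (≥ 8) |
|---|---|---|
| 7.5 | within | no |
| 8.0 | within | yes |
| 8.5 | above | yes |

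This takes the normal range to include its upper limit, which the SAP does not contradict. It applies to post-baseline readings in children not already markedly abnormal at baseline, because the others are not counted.

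**3. What the missing units leave open.** The documents do not say whether the laboratory reports concentrations or daily amounts, so both cases are shown.

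- *If concentrations:* concentration = excretion / volume. At constant excretion, halving the volume gives 1/0.5 = 2.0 times the value, and doubling it gives 1/2 = 0.5 times. A short collection at steady excretion and urine flow leaves the value unchanged.
- *If daily totals:* at equal excretion per kg, the weights in Protocol Attachment 2 (10 kg to above 40 kg) imply at least a 40/10 = 4-fold spread between children. A 16-hour collection handed in as 24 hours gives 16/24 = 0.67, a 33% shortfall.
- *Ratio to creatinine from the same sample:* volume and collection time multiply numerator and denominator by the same factor and cancel in both cases.

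The 4-fold and 33% figures belong to the second case only. The 16-hour example is an illustration, not a rate from the documents.

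**The case against.** The strongest reply is that the scaling point rests on silence. Collection details are left to the laboratory manual, and the laboratory may already report daily amounts or ratios. That stands: a reader might infer that the trial will analyse unscaled concentrations, and the documents do not show it. They show only that the SAP states no units and no derivation.

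Other stronger readings also fail:

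- *The 4-fold spread is the error in the arm comparison.* It is a spread between children. Randomisation is stratified by age group, SAP 3.4 adds summaries by four age groups, and change from baseline is taken within child. Much of the size difference is balanced or removed.
- *These urine markers are the only mechanistic evidence on stones.* Serum bicarbonate is measured, is among the key safety endpoints in Protocol 11.4 and has limits in Appendix 2. Sediment crystals are examined when the dipstick is abnormal.
- *High urine calcium cannot be counted at all.* Investigators record clinically relevant laboratory changes as adverse events, and SAP Appendix 3 includes hypercalciuria and raised urine calcium terms. Only the threshold-based count is missing. Appendix 3 has no urine citrate term, so the gap is wider there.
- *Every reading of 8.0 is contradictory.* Those already markedly abnormal at baseline are excluded from the count.

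It is also fair to say that the SAP makes stones a secondary objective and plans no formal testing, so these are descriptive tables. Observed and change summaries can still be produced without any limits. None of this supplies the missing limits or removes the overlap at pH 8.0.

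**Conclusion.** Two defects are established from the text. SAP 7.10 promises threshold-based 24-hour urine results that cannot be produced for calcium, citrate, phosphorus or creatinine: four of five analytes, or all five if the pH row is for dipstick only. The pH limits also put 8.0 in two opposite classes. The number of readings affected depends on the frequency of 8.0 and the reporting steps, which the documents do not give; means and changes in pH are unaffected.

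The third element is an omission: no units, volume or creatinine scaling is specified. Its practical size depends on what the laboratory reports. The point is worth correcting because these markers are named in the stone rationale and creatinine is already measured in the same collection. It does not threaten the growth or bone analyses.

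**What to change.** In SAP 7.10, Appendix 2 and the urinalysis table:

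- Set markedly high pH at > 8 so that it excludes the upper normal value, and say whether the row applies to dipstick pH, 24-hour pH or both.
- Add pre-specified, age-appropriate 24-hour urine limits for at least calcium and citrate. If laboratory limits are used, write an explicit exception to the SAP-ranges-only rule. The documents do not show whether the laboratory holds such limits, so this must be confirmed first.
- State the units of each 24-hour analyte.
- Summarise calcium/creatinine, citrate/creatinine and phosphorus/creatinine (observed and change) by arm and visit. These go in addition to the reported values, since change from baseline in urine laboratory tests is a key safety endpoint in Protocol 11.4.

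The cost is SAP wording, a few derived variables and one extra descriptive table; no new measurement is needed. The main drawback is that creatinine excretion varies with age and muscle mass, so any limits on the ratios must be age-specific.
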